In the setting of the kidney allograft there are therefore at least two factors driving glomerular volume increase potentially leading to hypertrophic podocyte stress and glomerulosclerosis. (i) The compensatory kidney hypertrophy that occurs in the transition from the 2 kidney to the 1 kidney state as the single allograft picks up twice the normal work load. (ii) Post-transplant weight gain that is associated with additional glomerular volume increase driven by growth factors, nutrients and other pathways. (iii) Development of overt diabetes will further amplify growth signaling and glomerular enlargement. **We hypothesize that the combination of these factors drives the observed accelerated podocyte detachment rate leading to progressive glomerulosclerosis and shorter-than-expected allograft half-life.** If this hypothesis is correct then slowing the rate and amount of glomerular volume increase should reduce the degree of hypertrophic stress and rate of podocyte detachment leading to preservation of glomerular structure and function. This hypothesis has been directly validated in a nephrectomy model in rats where even quite modest caloric intake reduction (CIR) is protective of development of glomerular enlargement, podocyte hypertrophic stress, proteinuria, glomerulosclerosis and kidney failure. **As a first step towards implementing these concepts in humans we will perform a small pilot study designed to test the feasibility of conducting such a study as well as to test the hypothesis that modest CIR can reduce the amount and rate of glomerular growth that accompanies kidney transplantation.**

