Secondary Endpoints: Monitor at months 3 and 12, differences in glomerular filtration rate (GFR) using both creatinine (modified diet in renal disease) as well as serum cystatin C based equations (to account for the possibility that caloric restriction may also affect lean muscle mass and thus creatinine levels), urine protein to creatinine ratio (UPCr), differences in weight as well as glycosylated hemoglobin (HbA1c).

Study Eligibility

Patients presenting for living or deceased kidney transplantation at the University of Michigan Hospital.

Inclusion Criteria:

- Recipients of Living and Deceased donor kidney transplants where a post perfusion biopsy is obtained
- BMI ≥ 25 kg/m² at the time of randomization
- Age range: 18-70
- Immediate graft function.
- Standard triple immunosuppression (Tacrolimus, Mycophenolate Mofetil, Prednisone) with or without induction.
- No experimental drugs.
- Have smartphone or active internet connection at home.

Exclusion Criteria :

- Patients who do not meet eligibility/inclusion criteria or who do not provide consent.
- Patients on dual antiplatelet agents or who are on oral anticoagulation
- Patients who did not receive a post-perfusion biopsy
- Early post-op wound complications
- Patients who have had Bariatric Surgery (concerns for malnourishment)
- Patients who will be taking Angiotensin Converting Enzyme Inhibitors (ACEi) or Angiotensin Receptor Blockers (ARBs) within the first 3 months' post-transplant

Study Setting, Patient Enrollment and Randomization

Study Setting: Single center study at the University of Michigan Hospital where approximately 200 kidney transplants are performed every year

Patient Enrollment: Patients who meet the inclusion criteria and provide written informed consent after adequate explanation of the risks and benefits will be randomized in a 1:1 fashion to the modest CIR or the standard of care arm. Study participation will end 12 months after transplantation.

Study procedures, Interventions, tests follow up, concurrent therapies and study end

Study Procedures: Patients who consent, will be randomized to modest CIR or the standard of care arm. The standard of care arm patients will obtain dietary guidance per current University of Michigan Transplant Center policy, where a one time face-to-face visit is provided in the first month after kidney transplant and then as requested by the patient or referred by physician.

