All pertinent demographic variables including age, gender, race, weight, height, body surface area etc. Donor information on age, gender, weight, race will also be recorded. Type of induction therapy, maintenance therapy at time of discharge and any changes over the first year will be recorded with reason for change. At all prespecified time points recipient vital signs including weight, development of post transplant diabetes,initiation of hypoglycemic agents, rejection will be recorded.

Concurrent Therapies

Immunosuppression: Induction agents will be used according to center protocol. Experimental agents will not be used. Maintenance immunosuppressive therapies will be according to center protocol (Thymoglobulin, Mycophenolate Mofetil and Prednisone). Use of mammalian target of rapamycin inhibitor (mTORi) such as Sirolimus or Everolimus will be discouraged until 3 months after kidney transplantation, unless there is a compelling clinical reason.

Others: No Angiotensin Converting Enzyme Inhibitors (ACEi) or Angiotensin Receptor Blockers (ARBs) are allowed in patients in the study until after 3 months' post-transplant at which time the timing of initiation will be deferred to the attending physician taking care of the patient.

Hypertension, dyslipidemia and other medical conditions will be treated per the UMHS transplant center's cardiovascular disease prevention and treatment protocols and determined by individual transplant physicians and surgeons caring for the given patients.

End of Study

Completion of study: The study will end 12 months after transplantation. Patients will continue to receive care for their medical conditions related or not to the study as per the UMHS transplant center.

Study Withdrawal: Patients or their physicians can withdraw the patient from the study at any time.

Data collection and Storage: The proposed study intends to use a web-distributed data entry clinical research data management on the Research Electronic Data Capture (RedCap) platform.

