Statistical considerations and analytical plan: Previous animal studies have shown that approximately 5 animals in each arm (dietary restriction vs. ad lib) has been sufficient. However, given lack of any previous data in humans and higher expected variability, we plan on recruiting 15 patients in each arm in this pilot trial. Further trials will use data obtained from this trial to determine the number of patients necessary to adequately power future studies. The unpaired "t" test will be used to compare differences in glomerular: volume, DAPI positive nuclei, Ki67 positive nuclei, TLE4 positive nuclei. Differences in means of proportions will be measured z test . A linear regression model will be utilized to quantify the relationship between the continuous variables. Best-fit curve estimation, including quadratic and cubic models, will be utilized, if necessary, to demonstrate nonlinear associations between two continuous variables.

Safety Monitoring:

Although we do not anticipate any adverse events due to caloric restriction, all adverse events including serious adverse events that could be related or possibly related will be reported. Reducing caloric intake may cause hypoglycemia in some individuals.

Potential Pitfalls: Patient may not follow instructions on diet leading to higher than desired caloric intake causing the study endpoints to be affected. However, this may offer further insight into study design feasibility and allow us to make appropriate changes for future studies.

As glomerular hypertrophy can also be driven by donor and recipient body size mismatch we have tried to minimize that possibility by using the average BMI groups for both donors and recipients (BMI:25-30 kg/m²). Other interventions that can affect glomerular hypertrophy including the use of ACEi/ARBs, mTORi which will be avoided in the first 3 months post transplant. Theoretically , the use of antiproliferative drugs used in transplantation may limit cell growth and thus we may not see the full benefit of reducing hypertrophy by dietary interventions. However, since the control and the intervention arms are on the same immunosuppressive agents, we believe that the effect of caloric restriction on glomerular growth would still be possible to observe.

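### Diabetes at transplant is neither a stratum nor a covariate, which costs precision in the HbA1c comparison and possibly in Aim 1 glomerular growth

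*Combined protocol and SAP*

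**What the plan says.** All references are to the combined protocol and SAP.

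- **Mechanism.** After compensatory hypertrophy and weight gain, the Specific Aims list a third influence on glomerular volume: "Development of overt diabetes will further amplify growth signaling and glomerular enlargement".
- **Eligibility.** No inclusion or exclusion criterion under Study Eligibility mentions diabetes. The nearest exclusions are "Patients who have had Bariatric Surgery (concerns for malnourishment") and "Patients who will be taking Angiotensin Converting Enzyme Inhibitors (ACEi) or Angiotensin Receptor Blockers (ARBs) within the first 3 months' post-transplant". Recipients with diabetes at transplant can therefore enter.
- **Allocation.** Under Patient Enrollment, consenting patients "will be randomized in a 1:1 fashion to the modest CIR or the standard of care arm". No stratum, block or minimisation is described.
- **Size.** Under Statistical considerations, "we plan on recruiting 15 patients in each arm in this pilot trial". The same section says that the data will be used to size later trials.
- **Analysis.** That section names an unpaired t test for glomerular volume and the cell counts. Linear regression is foreseen only for relations between continuous variables. No test is named for HbA1c and no covariate is named for any comparison.
- **Glycaemic outcome.** The Secondary Endpoints include "differences in weight as well as glycosylated hemoglobin (HbA1c") at months 3 and 12, without separation by diabetes status at entry.
- **Recorded items.** The section on tests and follow-up records "development of post transplant diabetes" and the start of hypoglycaemic agents. Its list of recipient variables is open-ended and does not name diabetes at transplant.
- **Pitfalls.** Potential Pitfalls discusses body-size mismatch, ACEi/ARB, mTOR inhibitors and antiproliferative drugs as influences on hypertrophy. Diabetes is not discussed there.

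**The concern.** HbA1c depends strongly on whether a patient already has diabetes. Pooling the two kinds of patient without a stratum or covariate puts the difference between them into the error term. It also lets a chance imbalance move the estimated arm difference. With 15 per arm such imbalances are common.

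The same may apply to glomerular growth, the Aim 1 primary endpoint, if diabetes present at transplant acts through the growth signalling that the plan ascribes to new diabetes.

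This matters beyond the pilot because its estimates and SDs are meant to size later trials. If diabetes at transplant is not recorded as a study variable, the problem cannot be examined afterwards either.

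**Working it through.** **The plan's own figure.** The 15 per arm cannot be reproduced. It rests on animal work with about 5 per arm and on an expectation of higher variability in humans; no alpha, power, effect size or SD is given. For orientation, at two-sided 0.05 (assumed) 15 per arm has 80% power for a standardised difference of about 1.06 (t test, 28 df). The Aim 1 paragraph speaks of randomising 15 patients; I use the 30 in total and 15 per arm given under Study Design and Statistical considerations.

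**Inputs not in the documents (assumed, shown as ranges).** Diabetes prevalence, the effect of diabetes on growth, and all SDs.

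**1. Chance imbalance.** The numbers of diabetic patients in the two arms are X and Y, independent Binomial(15, p).

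| p | P(difference ≥ 3) | P(difference ≥ 4) | P(difference ≥ 5) |
|---|---|---|---|
| 20% | 25% | 11% | 4% |
| 30% | 32% | 16% | 7% |
| 40% | 35% | 19% | 9% |
| 50% | 36% | 20% | 10% |

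**2. Shift in the Aim 1 contrast.** Shift = (imbalance / 15) × extra growth in diabetic patients. With 5 to 15 percentage points of extra growth (assumed), an imbalance of 3 gives 3 × 5/15 = 1.0 to 3 × 15/15 = 3.0 points. An imbalance of 4 gives 1.3 to 4.0 points. The Background expects about 25% total growth by 3 months. The better yardstick is the standard error of the arm difference, SD × √(2/15). At an assumed SD of 15 to 30 points this is 5.5 to 11 points, so a shift of 1 to 4 points is 0.09 to 0.73 standard errors.

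**3. Power for Aim 1.** Take a treatment effect of 1.0 within-group SD and a diabetes effect of e SD. The unadjusted SD is √(1 + p(1−p)e²), the noncentrality is √(15/2) divided by that SD, and there are 28 df. The adjusted analysis has noncentrality √(15/2) = 2.74 and 27 df.

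| p | e | Unadjusted SD | Power unadjusted | Power adjusted |
|---|---|---|---|---|
| 20% | 0.5 | 1.020 | 73.6% | 75.2% |
| 40% | 0.5 | 1.030 | 72.8% | 75.2% |
| 20% | 1.0 | 1.077 | 69.0% | 75.2% |
| 40% | 1.0 | 1.114 | 66.1% | 75.2% |

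The gain runs from 75.2 − 73.6 = 1.6 to 75.2 − 66.1 = 9.1 points.

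**4. HbA1c.** Assume an SD of 0.4 without and 1.2 with diabetes, and a mean gap m of 1.0 to 2.0. The mixed SD is √((1−p)·0.4² + p·1.2² + p(1−p)m²).

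- p = 20%, m = 1.0: √(0.128 + 0.288 + 0.160) = 0.76. The difference detectable with 80% power is 1.06 × 0.76 = 0.80.
- p = 40%, m = 2.0: √(0.096 + 0.576 + 0.960) = 1.28. The detectable difference is 1.35.
- Adjustment removes only the last term. The SD falls to √0.416 = 0.64 and √0.672 = 0.82, and the detectable difference to about 0.68 and 0.87.
- An imbalance of 4 in 15 shifts the unadjusted contrast by 4/15 × m = 0.27 to 0.53.

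**The case against.** The strongest reply is that randomisation already deals with this. It does in one sense: the expected imbalance is zero, the estimate is unbiased on average, and the t test keeps its type I error. At prevalences of 20% to 50% the arms differ by fewer than 3 diabetic patients in 64% to 75% of trials. This part stands and limits the point to precision and to the reading of one small trial.

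Second, the Specific Aims speak of developing overt diabetes. The Background links post-transplant diabetes to weight gain, and the Aims list it among the things the diet may affect. New diabetes may therefore lie on the diet's causal path. A reader might infer that the plan itself names pre-existing diabetes as a driver of the primary endpoint. It does not; that extension is an inference from mechanism. This too stands, and it is why only status at transplant should be used for adjustment.

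Third, few strata fit into 30 patients, and donor type or body-size mismatch could compete for the place. The documents do not rank them. The clearest argument for diabetes is HbA1c, where its relevance does not depend on the Aim 1 inference.

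Other stronger readings are not supported:

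- A reader might infer that the post-transplant diabetes rate has a wrong denominator. The plan only records new diabetes; it defines no rate and does not list it as an endpoint. HbA1c is the only listed glycaemic endpoint.
- A reader might infer that the safety text conflicts with the minimal-risk statement. Safety Monitoring says "Reducing caloric intake may cause hypoglycemia in some individuals", and Protection of Human Subjects repeats the warning. There is nothing to reconcile.
- A reader might infer that any HbA1c difference would mainly show who was diabetic at entry. The calculation shows a possible shift and a larger SD, not that.

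**Conclusion.** The point holds as a matter of precision. Patients with diabetes at transplant are eligible, allocation is plain 1:1, and nothing in the analysis takes account of their status. The loss is clearest for HbA1c. For Aim 1 it depends on whether pre-existing diabetes affects early glomerular growth, which the documents do not say.

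An imbalance of 3 or more diabetic patients would arise in 25% to 36% of trials, and the gain in Aim 1 power from adjustment is about 2 to 9 points. The first range rests on an assumed prevalence of 20% to 50%. The second rests on a prevalence of 20% to 40%, a 1-SD treatment effect and a diabetes effect of 0.5 to 1.0 SD, all assumed. The ACEi/ARB exclusion may lower the prevalence by an amount that the documents do not give. The design is not biased and the pilot is not invalid; this is a cheap improvement worth making.

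**What to change.** 1. Record diabetes at transplant (yes/no) from the chart for every patient.
2. Use it as the only stratum, with permuted blocks of varying size because the trial is open. If enrolment has begun, leave the allocation alone and prespecify it as one covariate before any outcome comparison by arm.
3. Analyse glomerular volume change and HbA1c by linear models with arm and diabetes at transplant. Do not adjust for diabetes that develops after randomisation.
4. Show HbA1c by baseline status descriptively. At 20% to 50% prevalence there would be about 15 × 0.2 = 3 to 15 × 0.5 = 7.5 diabetic patients per arm, too few for separate tests.

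The cost is one degree of freedom (28 to 27), one recorded variable and a slightly more complex allocation list; incomplete blocks may leave the arms a patient or two away from 15 each. Eligibility, sample size and study procedures do not change.

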Weight gain after kidney transplantation affects 50-90% of kidney allograft recipients. By one-year post transplantation, on average recipients gain about 10% of their pre-transplant body weight and 50% of all recipients are obese ($BMI > 30 \text{ kg/m}^2$) (1, 2). Increased weight gain after transplantation is associated with reduced allograft survival by poorly understood mechanisms (3). In model systems we have shown that weight gain is associated with increased glomerular volume (i.e. filtration surface area) that drives hypertrophic podocyte stress resulting in progressive loss of podocytes from glomeruli (4). We have also shown that podocyte loss itself drives progressive glomerulosclerosis and kidney failure (5). By 3-months post transplant kidney allograft glomeruli have increased their glomerular volume by 20-25% and experience a 6-fold increase in rate of podocyte detachment, ranging from a 2-fold increase in stable allografts to a 10-20 fold increase in transplant glomerulopathy (6). In simulation studies these factors can quantitatively account for the observed shorter-than expected allograft half-life at about 15 years and the powerful donor age effect on allograft survival (7). Compatible with this concept glomerulosclerosis is a significant contributor to late allograft failure as demonstrated by several reports (8, 9).

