Aim 1: Test the hypothesis that modest CIR (~500 kcal/day) reduces the glomerular growth rate associated with kidney transplantation. For this pilot study, we will randomize 15 overweight or obese patients ($BMI > 25 \text{ kg/m}^2$) patients to dietician guided modest CIR or standard of care. All patients will undergo standard protocol biopsy at time 0 and 3 months post-transplantation. We will compare the difference in glomerular volume, number of Ki67 positive (actively dividing) glomerular cells, DAPI positive (all glomerular cell nuclei) and TLE4 positive (podocyte nuclei) intraglomerular cells from at least 8 glomeruli/patient. In those patients in whom the CIR protocol reduced post-transplant weight gain we expect to see lower glomerular growth rate as demonstrated by reduced glomerular volume increase and a lower number of Ki67 positive intraglomerular cells. As podocytes don't divide we also expect to see a lower proportion of podocytes (TLE4 positive/total DAPI positive nuclei) reflecting the increased growth rate of non-podocyte cells in the glomerulus.

Aim 2: Test the hypothesis that modest CIR reduces podocyte hypertrophic stress as assessed by a reduction in the urinary podocyte detachment rate. For this aim we will collect urine samples at the time of 3-month protocol biopsies and compare the urinary podocin to creatinine ratio as well as markers of podocyte "hypertrophic stress" including the urine podocin to nephrin ratio across both groups (10). We expect a lower urinary podocyte detachment rate as well as lower urine podocin to nephrin ratio in the intervention arm.

These studies will provide insight into the feasibility of conducting larger clinical studies using CIR in the early post-transplant period. Further, they may provide insights into the mechanistic role of caloric restriction on post-transplant glomerular growth, as well as their impact on reducing post-transplant weight gain, post-transplant diabetes mellitus and hypertension, all of which alone or in combination can affect allograft and patient survival. With the average cost of dialysis at 100,000 USD/year, even a 1-year improvement in allograft longevity of the approximately 15,000 kidney transplants performed every year translates into cost savings of approximately 1.5 billion dollars.

BACKGROUND INFORMATION

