1. Yang et al. JASN 2015. Demonstrates that allograft recipients have a 6-fold increased rate of podocyte detachment and that post-transplantation kidney allografts have an increased glomerular volume and reduced podocyte density, and podocyte number per glomerulus decreases in association with development of transplant glomerulopathy(6).
2. Naik et al. JCI Insight 2016. Demonstrates that the podocyte depletion hypothesis can account for the unexpectedly short allograft half-life and the donor-age effect on allograft outcomes(7).
3. Nishizono et al. JASN, manuscript accepted for publication. Demonstrates in a rat model that CIR reduces glomerular enlargement, podocyte stress, podocyte reduction rate and glomerulosclerosis

By other investigators:

- Previous dietary intervention trials in clinical transplantation demonstrate feasibility in reducing weight gain post-transplant. A previous study compared patients who received weekly dietary advice to identical historical controls. At baseline both groups had identical weights. By 4 months post-transplant the intervention group had gained on average 2 kilograms compared to 7 kilograms in the historical control. By the end of the first year, the intervention arm had gained 6 kilograms compared to the 12 kilograms in individuals that received standard post-transplant dietary advice(11).

STUDY DESIGN AND METHODOLOGY

Prospective randomized single center clinical trial with un-blinded endpoint evaluation. The study is a pilot interventional trial comparing the impact of modest caloric intake reduction on glomerular growth and podocyte parameters after kidney transplantation. This pilot study plans to enroll 30 patients at the University of Michigan. We will follow patients for 12 months after their transplant.

Study Endpoints

Primary Endpoint for Aim 1: Assess differences in change of glomerular volume from immediate post perfusion biopsies to those obtained at 3 months between both arms. Further we will also investigate the

differences in number of Ki67 positive, DAPI positive (all glomerular cells), TLE4 positive (all podocytes) intraglomerular cells from at least 8 glomeruli/patient.

Primary Endpoint for Aim 2: Assess differences in urinary podocyte detachment rate (measured as urine podocin mRNA to creatinine ratio) as well as markers of podocyte “hypertrophic stress” such as urine podocin to nephrin ratio.

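### Donor age is recorded and tied by the plan to podocyte loss and graft outcome, but the comparison of arms of 15 does not adjust for it; the 3-month-only cell-count and urine measures are the most exposed

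*Combined protocol and SAP*

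**What the plan says.** **Population and allocation.** The Inclusion Criteria admit "Recipients of Living and Deceased donor kidney transplants where a post perfusion biopsy is obtained". Under Patient Enrollment, consenting patients "will be randomized in a 1:1 fashion to the modest CIR or the standard of care arm". No blocking, stratification or minimisation is described.

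**Size.** Study Design and Methodology says "This pilot study plans to enroll 30 patients at the University of Michigan", and the Statistical considerations say "we plan on recruiting 15 patients in each arm in this pilot trial". Aim 1 reads differently: "For this pilot study, we will randomize 15 overweight or obese patients". I use 15 per arm.

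**Analysis.** The Statistical considerations name an unpaired t test for glomerular volume and for the DAPI, Ki67 and TLE4 counts, and a z test for proportions. They name no specific test for the urine measures. The regression sentence concerns relations between continuous variables and does not describe an adjusted comparison of arms.

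**Donor age.** The Specific Aims say that simulation studies can account for "the powerful donor age effect on allograft survival" through glomerular enlargement and podocyte detachment. The Abstract and the list of the team's published work make the same link. Under Tests, Procedures and Follow up, "Donor information on age, gender, weight, race will also be recorded". Donor age then has no role in allocation or analysis, and donor type is not in that list.

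**Timing of measures.** The Aim 1 volume endpoint is the change from the post-perfusion biopsy to 3 months. TLE4, DAPI and Ki67 staining is described only for the 3-month biopsy, and urine is collected only then.

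**Other donor factors.** Potential Pitfalls addresses donor-recipient size mismatch through a BMI range of 25-30 for both. The eligibility criteria give only a lower BMI limit of 25 and do not mention donor BMI.

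**The concern.** The plan explains the donor-age effect on graft outcome by podocyte density and podocyte loss. Its endpoints (podocyte nuclei, glomerular cells, glomerular volume, urinary podocin) are close to that mechanism. If donor age predicts them, leaving it out has two costs. Donor-driven variation stays in the error term and widens the interval for the arm effect. And in a trial where the arms happen to differ in donor age, part of that difference appears in the arm contrast.

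A change from baseline removes stable donor differences in glomerular size from the volume endpoint. The cell counts and urine measures have no baseline value, so nothing in the plan does this for them. The pilot's estimates are also meant to size later trials, so an imprecise contrast or an SD inflated by donor variation would carry forward.

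**Working it through.** **No figure of the plan to reproduce.** The 15 per arm rests on animal precedent of about 5 per arm, with no effect size, SD, alpha or power. For scale: assuming two-sided 5% and 80% power, 15 per arm detects about 1.06 SD (noncentral t).

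**Inputs.** 15 per arm is from the documents. The correlation r between donor age and an outcome, the donor-age SD and the number of deceased donors are not given. They are assumed and shown as ranges.

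**1. Chance gap in mean donor age.** In SD units the arm difference has SE = sqrt(2/15) = 0.365.
- P(|gap| > 0.5 SD) = 2 × [1 − Φ(0.5/0.365)] = 17%, whatever the SD.
- In years, for an assumed donor-age SD of 10 to 15: SE = 3.65 to 5.48, and P(gap of 5 years or more) = 17% to 36%.
- If Aim 1's 15 were the total (arms of 7 and 8): SE = sqrt(1/7 + 1/8) = 0.518, and P(|gap| > 0.5 SD) is about 33%.

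**2. What a gap does to the unadjusted contrast.** The shift, in outcome SDs, is gap × r. A 0.5 SD gap shifts the contrast by 0.15 SD at r = 0.3 and 0.25 SD at r = 0.5. The type I error of the t test, conditional on the gap (simulation, 50,000 runs per setting), is:

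| Donor-age gap | r = 0.3 | r = 0.5 | r = 0.7 |
|---|---|---|---|
| 0.5 SD | 5.6% | 7.1% | 8.0% |
| 0.73 SD (about 2 SE, roughly 5% of trials) | 7.8% | 12.9% | 20.6% |

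Averaged over all allocations, the type I error stays nominal.

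**3. Precision gained by adjusting for donor age.** Variance ratio, adjusted to unadjusted = (1 − r²) × (1 + 1/26). The second factor is the expected price of estimating one covariate with 30 patients.

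| Assumed r | Variance ratio | Reduction |
|---|---|---|
| 0.2 | 0.96 × 1.0385 = 0.997 | 0.3% |
| 0.3 | 0.91 × 1.0385 = 0.945 | 5.5% |
| 0.4 | 0.84 × 1.0385 = 0.872 | 13% |
| 0.5 | 0.75 × 1.0385 = 0.779 | 22% |

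Break-even is at 1 − r² = 26/27, so r = sqrt(1/27) = 0.19. Below that, adjustment loses slightly. Power for a true 1.0 SD effect is 75% unadjusted; adjusted it is 75%, 78% and 85% at r = 0.2, 0.3 and 0.5.

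**4. Donor type as a second term.** With two covariates the price factor is 1 + 2/25. If donor type adds nothing, the reductions become 1 − 0.91 × 1.08 = 1.7%, 1 − 0.84 × 1.08 = 9.3% and 1 − 0.75 × 1.08 = 19% at r = 0.3, 0.4 and 0.5. Stratified allocation would lessen that penalty. For chance imbalance, with 10 to 20 deceased donors among 30 and arms fixed at 15:15, the arms differ by 4 or more with probability 13-27% (hypergeometric, every integer in the range).

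**The case against.** The strongest case is that this is a randomised pilot, the t test is valid, and the prognostic premise is not in the documents. Much of that stands.

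- **A reader might infer that the plan calls donor age a strong predictor of the 3-month measures.** It does not. The effect is on graft survival and outcomes, and the support cited is simulation work. The step to glomerular growth, cell counts or urinary podocin is an inference from the plan's mechanism, and no correlation is given.
- **A reader might infer that mixing living and deceased donors confounds the trial.** No section links donor type to any endpoint, so the 13-27% describes a variable whose prognostic value is not shown. The requirement for immediate graft function also narrows donor variation somewhat.
- **A reader might infer that imbalance is likely or the test invalid.** A gap above 0.5 SD occurs in a minority of trials, and the overall error rate is nominal.
- **A reader might infer coin-flip allocation**, under which an exact 15/15 split has probability 14% and a split of 20:10 or worse 10%. The protocol does not state its sequence method, and a planned 15 in each arm is compatible with restricted allocation. Even 20:10 raises the variance of the contrast by only 12.5%: (1/20 + 1/10)/(2/15) = 1.125.
- **The volume endpoint is a within-graft change**, so it is less exposed than the other measures.

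Pilot status does not dispose of the point. Aims 1 and 2 state hypothesis tests, the results feed later sample sizes, and the covariate is already collected.

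**Conclusion.** The point holds as a modest improvement in precision and protection against conditional bias, not as a flaw that invalidates the comparison. The plan points to donor age through its own mechanism, records it, and leaves it unused in a comparison of 15 against 15. The measures with no baseline value have most to gain.

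The size depends on the unknown correlation: negligible at 0.2, small at 0.3, and worthwhile at 0.4 to 0.5. It also rests on 15 per arm, a roughly linear relation and no dropout. Donor type is a secondary matter, because the documents do not show it to be prognostic.

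**What to change.** Prespecify, in the Statistical considerations, a linear model with arm and donor age for the Ki67, DAPI, TLE4 and urine measures, and for change in glomerular volume. Report the arm effect as an estimate with a confidence interval, and keep the unadjusted t test as the sensitivity analysis. The cost is one of 28 error degrees of freedom, a slight loss if the correlation is below about 0.19, and SAP wording. No extra patients, visits or assays are needed.

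Optional and secondary: allocate by permuted blocks stratified by living or deceased donor, put that stratum in the model, and add donor type to the recorded variables. This costs randomisation-list set-up and a second degree of freedom.

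State the sequence method in either case, and reconcile the 15 patients in Aim 1 with the 30 given elsewhere.
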